5.4.6.4. Specular Microscopy

Central endothelial cell density (CECD) mean (cells/mm²) will be assessed using specular microscopy performed on the central cornea at Screening, Baseline, Week 16, Month 6, Month 9 and Month 12/Exit. At each examination, 3 measurements of CECD will be reported, and the average of the 3 measurements will be calculated and used for analysis. CECD at baseline and raw values and their changes from baseline will be summarized descriptively by visit and for last visit by treatment cohorts.

Note that the same model of the specular microscopy machine must be used for all patient visits. If a different model is used at post-baseline visit, the data will be excluded from the analysis.

The number and percentage of participants will be tabulated by loss categories for each visit, including the last visit (ie, last assessment), and during the entire study, eg, 15% loss (percent change from baseline $\leq -15\%$). The last visit of a participant for final analysis is defined as the assessment at exit visit (ie, the last assessment during the study).

By visit tabulation will be based on the analysis value. A participant will be counted in a loss category for the entire study if any assessment during the study meeting the criteria. The loss categories are listed but not limited to the below:

- Percent change from baseline $> -10\%$
- Percent change from baseline $\leq -10\%$
- Percent change from baseline $\leq -15\%$
- Percent change from baseline $\leq -20\%$
- Percent change from baseline $\leq -30\%$
- Percent change from baseline $\leq -40\%$
- Percent change from baseline $\leq -50\%$

A listing of patients with $\geq 20\%$ CECD loss will be provided.

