a Eligibility criteria may be rechecked at any time prior to and during washout, at the discretion of the investigator.

b Washout in both eyes may begin after all screening procedures have been completed.

c Office visit procedures may be performed up to 7 days prior to Sleep Lab visit.

d Perform 24-hour Sleep Lab visit on a different day from all other Office visit study procedures.

e At sites where required by local institution or health authority, a serum test may be done, with negative results for all tests confirmed prior to the time of Bimatoprost SR administration. Pregnancy testing at Baseline is required regardless.

f Blood and urine samples are collected only at Screening unless a retest is necessary.

g Manifest refraction will be used to provide a correction for best-corrected visual acuity testing. At all study visits, if there is a 2-line or more reduction in visual acuity from the last best-corrected visual acuity performed, a repeat manifest refraction in both eyes and best-corrected visual acuity will be performed.

h At selected sites/selected participants only, anterior segment imaging may be performed in both eyes of consenting participants using Allergan-approved instruments.

i For a given participant, the same test methodology must be used for all visual fields performed at Screening, Baseline, and throughout the study.

j For a given participant, the same specular microscope model and analysis methodology must be used at Screening, Baseline, and throughout the study.

k Screening: participant number; Baseline: Hour 0 IOP; Day 1: enrollment after eligibility confirmation (may be done at end of Baseline visit if needed)

l All 24-hour Sleep Lab visit IOP exams will be performed with an Allergan-specified tonometer. Diurnal IOP measurements will be taken supine ≥ 5 minutes at rest then sitting ≥ 5 minutes at rest at 8:00 ± 30 min, 10:00 ± 30 min, 12:00 ± 30 min, 14:00 ± 30 min, 16:00 ± 30 min, 18:00 ± 30 min, 20:00 ± 30 min, and 22:00 ± 30 min. Nocturnal IOP measurements will be taken supine only ≥ 5 minutes at rest 00:00 ± 30 min, 02:00 ± 30 min, 04:00 ± 30 min, and 06:00 ± 30 min. Please see Procedure Manual for details.

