#### **9.4.2. Safety Analyses**

The safety analyses will be performed using the safety analysis set and will be fully defined in the SAP. General safety parameters will include AEs (including pregnancy) and vital signs. Ocular safety parameters will include visual fields, best-corrected visual acuity, conjunctival hyperemia, biomicroscopy, dilated ophthalmoscopy (including optic disc assessment), pachymetry, gonioscopy, and specular microscopy.

Ocular AEs and safety variables will be tabulated by cohort for the study eye and fellow eye, and nonocular safety variables will be summarized at the participant level.

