5.4. Safety Analysis

Descriptive statistics will be used to summarize the safety data by cohorts based on the SAF. The safety parameters will include the following non-ocular safety parameters: non-ocular AEs and vital signs; ocular safety parameters: visual field examination, visual acuity, macroscopic conjunctival hyperemia assessment, biomicroscopy, dilated ophthalmoscopy (including optic disc assessment), pachymetry, gonioscopy (including angle assessment), and specular microscopy. Results from ocular safety assessments will be summarized by participants and listed, including scheduled and unscheduled assessments (if any). The results will be presented by treatment cohorts for the study eye and pooled treatment cohorts for the fellow eye. Unless

otherwise stated, the last nonmissing safety assessment before the first dose of study treatment will be used as the baseline for all analyses of that safety parameter.

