6.3.2. Repeated or Unscheduled Assessments of Safety Parameters

If a participant has repeated assessments before the administration of treatment, unless otherwise stated, the results from the latest non-missing assessment made prior to the start of the study treatment will be used as baseline. If end-of-study assessments are repeated or if unscheduled visits occur, the last non-missing postbaseline assessment will be used as the end-of-study assessment for generating summary statistics. However, all postbaseline assessments will be used for safety evaluation, and all assessments will be presented in the data listings.

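### Fellow-eye endothelial cell density is pooled over both cohorts, so the Month 12 and whole-study reference for the implant eyes can mix about 8-week with 12-month follow-up

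*SAP*

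**What the plan says.** Central endothelial cell density (CECD) is "performed on the central cornea at Screening, Baseline, Week 16, Month 6, Month 9 and Month 12/Exit", which gives two pre-dose and four post-dose exams. The schedules of activities mark both eyes at each of them. For a given participant, "the same specular microscope model and analysis methodology must be used at Screening, Baseline, and throughout the study".

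On reporting, SAP 5.4.6.4 states that "CECD at baseline and raw values and their changes from baseline will be summarized descriptively by visit and for last visit by treatment cohorts" and names no eye. The eye rule is in SAP 5.4, which lists specular microscopy among the ocular parameters: "The results will be presented by treatment cohorts for the study eye and pooled treatment cohorts for the fellow eye". Protocol 9.4.2 reads differently: "Ocular AEs and safety variables will be tabulated by cohort for the study eye and fellow eye". SAP 6.4 reports no departures from the protocol's analyses.

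Three further rules bear on the point:
- Protocol 4.4 and SAP 1.2.4 let LUMIGAN participants leave after the Week 8 Sleep Lab visit, with the Month 12 assessments done at exit.
- SAP 6.3.1 summarizes LUMIGAN exit assessments under Month 12/Study Exit whenever they occur.
- SAP 5.4.6.4 counts a participant in a whole-study loss category if any single assessment meets the cut-off.

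No within-participant comparison of study and fellow eye is planned for CECD.

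**The concern.** Allocation is not randomized, and the LUMIGAN cohort has five participants who may stop at Week 8. The best reference for 12-month corneal safety is therefore the same participant's other eye, imaged on the same days under the same instrument rule. A reader of the CECD tables will set the Bimatoprost SR study-eye column beside the fellow-eye column.

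Pooling weakens that comparison in two ways. It places eyes with different follow-up lengths in one Month 12 row, and eyes with one chance and eyes with four chances to cross a cut-off in one whole-study row. It also gives up the pairing that would remove any drift shared by the two eyes. With no true implant effect, the mismatch pushes the fellow-eye rows toward less loss, so the implant eyes look relatively worse.

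**Working it through.** The documents give no sample size, error rate or measurement-error figure for CECD, so there is no plan figure to reproduce.

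**Inputs from the documents.** There are 5 LUMIGAN participants, and 25 to 30 in the Bimatoprost SR cohort with at least 20 evaluable. There are four scheduled post-dose CECD exams for a completer. A LUMIGAN participant leaving after Week 8 has one.

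**Assumptions.** There is no true implant loss. Exam-to-exam error is independent and normal with a coefficient of variation (CV) of 3%, 5% or 7%, after the averaging of three readings within an exam. Shared drift is 0% to 2% per year. All five LUMIGAN participants leave at about Day 56. Between 20 and 30 Bimatoprost SR participants contribute.

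**1. Share of short follow-up in the pooled Month 12 fellow-eye row.** Share = 5/(5 + n).
- n = 20: 5/25 = 20.0%
- n = 25: 5/30 = 16.7%
- n = 30: 5/35 = 14.3%

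**2. Whole-study row at -10%.** Let p4 be the chance that at least one of four exams reaches -10%, and p1 the chance for one exam (simulation, 400,000 eyes per setting, zero drift). The pooled fellow-eye rate is p4 minus the gap, where gap = share × (p4 − p1).

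| CV | p4 | p1 | Gap, 30 SR (× 0.143) | Gap, 20 SR (× 0.200) | Pooled fellow-eye rate |
|---|---|---|---|---|---|
| 3% | 2.35% | 0.68% | 0.24 points | 0.33 points | 2.0% to 2.1% |
| 5% | 19.61% | 6.92% | 1.81 points | 2.54 points | 17.1% to 17.8% |
| 7% | 36.00% | 14.46% | 3.08 points | 4.31 points | 31.7% to 32.9% |

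Unpooled Bimatoprost SR fellow eyes would have p4, the same as the study eyes, and the gap would vanish.

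**3. Month 12 mean.** Drift missing from the pooled fellow-eye mean = share × annual drift × (360 − 56)/360 = share × annual drift × 0.844. At 2% per year this is 0.24 points (0.143 × 2 × 0.844) to 0.34 points (0.200 × 2 × 0.844). At 1% it is half that, and at zero drift it is nil.

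**4. Other rows.** The last-visit row is exposed as Month 12 is, because the exit exam is each participant's last. If all five leave after Week 8, the Week 16, Month 6 and Month 9 rows contain Bimatoprost SR fellow eyes only and are not affected.

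**5. Paired mean difference.** With 2% per year shared drift and CV 5%, the mean Month 12 study-eye change is -1.8% and the mean study-minus-fellow difference is 0.0%. At CV 5% and zero drift the SD of change rises from 7.1% to 10.1%, a factor of about 1.4. For n = 20 and t = 2.093, the 95% half-width is 2.093 × 7.1/√20 = 3.3 points for the study eye and 2.093 × 10.1/√20 = 4.7 points for the difference. If the difference were put through the -10% cut-off at any visit, 37.4% of pairs would cross it, against 19.6% of single eyes. Pairing is therefore useful for means and harmful for cut-offs.

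**6. Two-exam baseline.** Using the mean of Screening and Baseline at CV 5% lowers the -10% whole-study rate from 19.6% to 15.2%. The 4.4-point fall is 1.1 eyes in 25 or 1.3 in 30. At -15% the rate goes from 3.9% to 1.9%, about half an eye.

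**The case against.** Fellow-eye results are reported. A reader might infer that the study eye is judged alone, but SAP 5.4 covers specular microscopy and presents the fellow eye, so background loss and drift will be visible. A reader might also infer that the plan reads noise and drift as implant-related loss. It does not: the tables are descriptive, there are no hypotheses, and no rule attributes a loss category to the implant.

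Protocol 9.4.2 leaves full definition of the safety analyses to the SAP, so pooling is open to the SAP authors. That is fair, but a presentation that differs from the protocol's should then appear in SAP 6.4.

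The fellow eye is an imperfect control. It receives standard of care, possibly laser or surgery. The 1800 cells/mm² minimum (inclusion 6.06) and the exclusions for recent intraocular surgery, corneal graft and glaucoma surgery (2.05, 2.06, 2.17) apply to the study eye only, although 2.07 screens both eyes for corneal abnormalities that would spoil the readings. If fellow eyes lose cells faster, subtraction understates implant loss, which is the wrong direction for a safety measure. This stands. It is why the difference should be supplementary and carry a stated limit.

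Differencing adds noise under independent errors. This also stands and confines it to means. Positively correlated errors between the eyes would reduce the penalty.

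It is tempting to go further and replace the single baseline. The SAP applies one rule throughout, that "the last nonmissing safety assessment before the first dose of study treatment will be used as the baseline". The Screening exam is earlier, precedes washout and carries the 1800-cell entry cut, and the gain is about one eye. The documents do not show the planned baseline to be wrong.

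**Conclusion.** The point holds as a presentation fault of modest size. Pooled fellow eyes do not follow protocol 9.4.2, SAP 6.4 does not record the difference, and the pooled Month 12, last-visit and whole-study rows can be a mismatched reference for the Bimatoprost SR study eyes. The short-follow-up share is 14% to 20% if all five LUMIGAN participants leave after Week 8, and proportionally less if fewer do. The resulting false gap at -10% in the whole-study row is 0.2 to 4.3 points over an assumed CV of 3% to 7%. The effect on the Month 12 mean is at most about 0.3 points for drift up to 2% per year. These figures rest on assumed noise and drift and on the two cohorts' fellow eyes behaving alike. The text mismatch and the mixing of follow-up do not depend on them.

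**What to change.** 1. In SAP 5.4.6.4, name the eyes and present Bimatoprost SR fellow eyes unpooled beside the study eyes, with the same by-visit and last-visit summaries and the same loss categories.
2. Add a supplementary descriptive table for that cohort: the within-participant study-minus-fellow difference in percent CECD change at each visit, with its mean and 95% paired-t interval. Use it for means only, not for the cut-offs, and omit fellow eyes from the date of any laser or surgery.
3. State under the table that fellow eyes are not untreated controls and did not have to meet the study-eye corneal and surgical criteria, so the difference may understate implant loss.
4. Keep the last pre-dose exam as the primary baseline. The mean of Screening and Baseline is at most an optional sensitivity analysis.
5. If pooled fellow-eye tables are kept for other ocular parameters, record that in SAP 6.4.

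The cost is SAP wording and one or two tables from data already scheduled. The main downside is the wider interval: about 1.4 times that of the study-eye mean if the errors in the two eyes are independent.

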#### **4.4. End of Study Definition**

The end of the study is defined as the date of the last visit of the last participant in the study or last scheduled procedure shown in the SoA for the last participant in the study.

A participant assigned and treated with Bimatoprost SR is considered to have completed the study if he/she has completed all visits of the study to Month 12. At the Month 12/Study Exit visit, if the investigator determines that any safety concerns warrant participant follow-up, the participant may be followed post exit until safety concerns are resolved based on the investigator's discretion. Participants assigned and treated with LUMIGAN 0.01% may early exit the study after completion of the Week 8 Sleep Lab visit, if there are no safety concerns in the opinion of the investigator, and at which time all assessments performed at the Month 12/Study Exit visit should be performed.

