## 9.2. Sample Size Determination

The sample size is based on practical considerations. Approximately 35 participants will be enrolled: 25 to 30 in the Bimatoprost SR cohort and 5 in the LUMIGAN 0.01% cohort.

Twenty-five to 30 participants will be enrolled in the Bimatoprost SR cohort to achieve a minimum total of 20 evaluable participants, defined as participants with sufficient data at baseline and Week 8 to evaluate the 24-hour IOP-lowering effect of Bimatoprost SR. This assumes a premature discontinuation rate of up to 33%. Participants who prematurely discontinue from the study will not be replaced.

Participants will be assigned to the Bimatoprost SR or LUMIGAN 0.01% cohort by the investigator.

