1.2.4. End of Study Definition

The end of the study is defined as the date of the last visit of the last participant in the study or last scheduled procedure shown in the SoA for the last participant in the study.

A participant assigned and treated with Bimatoprost SR is considered to have completed the study if he/she has completed all visits of the study to Month 12. At the Month 12/Study Exit visit, if the investigator determines that any safety concerns warrant participant follow-up, the participant may be followed post exit until safety concerns are resolved based on the investigator's discretion. Participants assigned and treated with LUMIGAN 0.01% may early

exit the study after completion of the Week 8 Sleep Lab visit, if there are no safety concerns in the opinion of the investigator. For the LUMIGAN cohort, an exit visit will be performed after the Week 8 Sleep Lab visit where all assessments scheduled for the Month 12/Study Exit visit will be performed.

2. Statistical Hypotheses

There are no statistical hypotheses for this study.

3. Sample Size Determination

The sample size is based on practical considerations. Approximately 35 participants will be enrolled: 25 to 30 in the Bimatoprost SR cohort and 5 in the LUMIGAN 0.01% cohort.

Twenty-five to 30 participants will be enrolled in the Bimatoprost SR cohort to achieve a minimum total of 20 evaluable participants, defined as participants with sufficient data at baseline and Week 8 to evaluate the 24-hour IOP-lowering effect of Bimatoprost SR. This assumes a premature discontinuation rate of up to 33%. Participants who prematurely discontinue from the study will not be replaced. Participants will be assigned to the Bimatoprost SR or LUMIGAN 0.01% cohort [REDACTED].

4. Populations for Analysis

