5.4.6.3. Macroscopic Conjunctival Hyperemia

Macroscopic conjunctival hyperemia assessment will be performed at all scheduled visits except on the administration day. Conjunctival hyperemia severity is assessed as 0 (None), +0.5 (Trace), +1 (Mild), +2 (Moderate), +3 (Severe) or 'Not Evaluable.' These data will be summarized overall by treatment cohort and associated eye using the worst severity of hyperemia observed.

In addition, worst severity grade increases greater than 1 (worsening ie, a change from 0 to 2 and above, from 0.5 to 2 and above, or from 1 to 3 and above) in hyperemia from baseline will also be summarized overall and by treatment cohort. If the worst severity grade during a period is less severe compared to baseline, it will be considered as 'no increase.'

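### The entire-study counting rule for endothelial cell loss is wrong for the > -10% row, and the SAP drops the planned vital-sign summaries without declaring it

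*SAP*

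**What the plan says.** **Endothelial cell density.** SAP 5.4.6.4 has four scheduled post-baseline assessments (Week 16 and Months 6, 9 and 12/Exit). Percent change from baseline is tabulated by category for each visit, for the last visit and for the entire study. The by-visit table uses the analysis value. For the entire study: "A participant will be counted in a loss category for the entire study if any assessment during the study meeting the criteria". The list, introduced by "The loss categories are listed but not limited to the below", opens with change > -10% and continues with six thresholds (<= -10, -15, -20, -30, -40 and -50%). The first row has no exception. Some readings are dropped: "If a different model is used at post-baseline visit, the data will be excluded from the analysis". The section before it, SAP 5.4.6.3, handles repeated hyperemia grades with a single worst value: "These data will be summarized overall by treatment cohort and associated eye using the worst severity of hyperemia observed".

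**Vital signs.** Protocol 9.4.2 names vital signs as a general safety parameter, and Protocol 9.4.2.2 plans descriptive statistics by cohort for baseline and for change at each assessment. SAP 5.4 includes them among the non-ocular parameters to be summarised. SAP 5.4.3 says they are recorded but not analysed. SAP 6.4 states that nothing departs from the analyses planned in the protocol.

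**The concern.** A rule based on any qualifying assessment suits a loss threshold, because one reading at or below the threshold is enough to show that the loss was seen. The > -10% row points the other way. A reader will take it as the share of participants whose loss stayed under 10%, and for that every reading must qualify. Under the stated rule one good reading is enough, even if later readings show a loss of 10% or more. The error runs in the reassuring direction, on an assessment that both documents list as a safety measure.

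For vital signs, the SAP disagrees with itself and with the protocol on whether a planned summary will exist, and its statement of changes is not true. A programmer working from SAP 5.4 and one working from SAP 5.4.3 would deliver different outputs.

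**Working it through.** The documents give no figure to reproduce here. The first part is a logic check followed by one division; the second is a comparison of sections.

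**1. Rule by row.** Let x1 to xk be a participant's usable post-baseline percent changes.
- Threshold rows: some xi <= -t holds exactly when min(x) <= -t. The any-assessment rule therefore equals the worst-value rule.
- The > -10% row: some xi > -10 holds exactly when max(x) > -10. This classifies by the best value. The complement of <= -10% needs min(x) > -10.

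The two readings of the > -10% row differ only when max(x) > -10 and min(x) <= -10, which takes at least two usable readings.

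**2. Example.** Changes of -4, -8, -11 and -13% meet > -10% (at -4 and -8) and <= -10% (at -11 and -13). By the worst value, -13%, the participant belongs only in <= -10%.

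**3. Enumeration.** All four-reading profiles were formed on an 11-value grid from +5% to -60% containing every threshold: 11^4 = 14,641. Three grid values lie above -10% and eight at or below it, so the profiles with values on both sides number 14,641 - 3^4 - 8^4 = 14,641 - 81 - 4,096 = 10,464. The any-assessment and worst-value rules disagreed in exactly these 10,464 profiles for the > -10% row, and in 0 profiles for each of the six threshold rows. The grid is arbitrary, so the proportion says nothing about how often this will happen in the trial.

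**4. Size per affected participant.** SAP 5.1.1 takes percentages within each treatment cohort, SAP 5.4 bases safety on the safety analysis set, and SAP 4.1 defines that set as all treated participants. Protocol 9.2 gives the planned number: "Twenty-five to 30 participants will be enrolled in the Bimatoprost SR cohort". If all enrolled participants are treated, each one with values on both sides adds 100/n points to the > -10% row:
- n = 30: 100/30 = 3.3 points
- n = 25: 100/25 = 4.0 points

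**5. Who can be affected.** SR participants have up to four scheduled post-baseline readings. In the other cohort, Protocol 4.4 says "Participants assigned and treated with LUMIGAN 0.01% may early exit the study after completion of the Week 8 Sleep Lab visit", and SAP 1.2.4 says "For the LUMIGAN cohort, an exit visit will be performed after the Week 8 Sleep Lab visit". A LUMIGAN participant who leaves then has one scheduled post-baseline reading and cannot be double-counted on scheduled data.

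**6. What is unaffected.** By-visit and last-visit tables use one value per participant, so > -10% and <= -10% are complementary there. The listing of participants with at least 20% loss does not use the > -10% row.

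**7. Vital signs, side by side.**

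| Section | Position |
|---|---|
| Protocol 9.4.2, 9.4.2.2 | Summarised by cohort, with change from baseline |
| SAP 5.4 | Listed among summarised parameters |
| SAP 5.4.3 | Not analysed |
| SAP 6.4 | No changes from protocol |

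SAP 5.4 and 5.4.3 cannot both hold. If 5.4.3 governs, 6.4 is untrue.

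**The case against.** The SAP never labels the > -10% row as participants who never lost 10%. Its own worked example of a category is a loss threshold (15%), and a sensible programmer might treat > -10% as the complement of <= -10%. The threshold rows are nested, so rows adding to more than 100% are not in themselves an error. The intention may well have been sound, but the text does not carry it: the row is listed as a loss category, the rule covers every category, and literal coding gives the wrong count.

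A reader might infer that the table conceals cell loss. It does not. All six loss rows are correct, and anyone reaching a threshold appears in its row. The correct > -10% share equals 100% minus the <= -10% row, provided everyone in the denominator has a usable post-baseline reading. Missing readings or a change of microscope model could break that condition.

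A reader might also enlarge the per-participant effect by shrinking the denominator for dropout, citing Protocol 9.2: "This assumes a premature discontinuation rate of up to 33"%. That allowance concerns participants evaluable for 24-hour IOP at baseline and Week 8. Treated participants who leave early stay in the safety analysis set, and Protocol 7.2 asks for the exit procedures, which include specular microscopy, at their last visit.

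On vital signs, Protocol 9.4.2 leaves safety analyses to be fully defined in the SAP, and vital signs are in neither endpoint list (Protocol 3, SAP Table 1-1). Both facts limit the importance. Neither reconciles SAP 5.4 with 5.4.3, nor makes 6.4 true once a specifically planned summary is dropped.

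**Conclusion.** Both parts hold, as minor points of descriptive safety reporting.

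The entire-study rule is right for the six loss rows and wrong for > -10%. Each SR participant with values on both sides of -10% inflates that row by about 3.3 points (n = 30) to 4.0 points (n = 25). This rests on the treated cohort as denominator and on treated numbers equal to planned enrolment. The documents do not allow the number of such participants to be predicted; if there are none, the row is correct.

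The vital-sign contradiction is plain from the text and needs no assumption. No primary or secondary endpoint is affected by either part.

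**What to change.** **SAP 5.4.6.4.** Add one sentence: in the entire-study column, each participant is classified by the most negative usable post-baseline percent change, so that > -10% means every usable post-baseline assessment is above -10%. Leave the six loss rows as they are. This costs nothing beyond the wording and matches the worst-value approach of SAP 5.4.6.3.

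**Vital signs.** Preferably, restore the Protocol 9.4.2.2 by-cohort summary in SAP 5.4.3. The data are already collected, and the cost is one more descriptive table. Failing that, remove vital signs from the list in SAP 5.4 and declare the omission in SAP 6.4, which takes one or two lines.
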